### 8.3.3.2. Sensitivity Analysis of Primary Endpoint

Sensitivity analysis is planned if >5% of participants in any treatment group have missing data in the primary endpoint or the values could not be used due to the use of prohibited medications.

If any of the sensitivity analyses yields a result that is in a different direction from the result of the primary analysis, the nature of the discrepancy will be examined to clearly explain the discrepancy based on statistical principles and the discrepancy will be discussed in the CSR.

#### 8.3.3.2.1. Complete Data Analysis

A sensitivity analysis using only participants who have at least baseline and Day 84 values will be performed. The MMRM analyses proposed for the analysis of the primary outcome will be provided for change from baseline to Day 84. A plot showing the LS mean  $\pm$  SE bar over time within each treatment group will be provided.

#### 8.3.3.2.2. Control-Based Pattern Mixture Model Multiple Imputation (PMM-MI)

- A sensitivity analysis using control-based Pattern Mixture Model Multiple Imputation (PMM-MI) under the missing not at random (MNAR) assumption will be used to investigate the impact of missing data ([Lingling 2019, SAS Institute Inc.](#)). MNAR assumes the missingness depends on the unobserved study data and cannot be predicted solely based on participant's observed data.

Control-based PMM-MI under MNAR involves four steps as described below.

##### Step 1. Assessing the pattern of missing data

To investigate the pattern of missing data, 'ods output misspattern' will be used in the MI procedure of the SAS system (PROC MI). The imputation method will be based on the observed pattern of missing data and amount of missing data. The pattern of missing data will be assessed as monotone or arbitrary.

##### Step 2. Turning the arbitrary missing patterns to monotone missing patterns under MAR assumption

If a mixture of non-monotone and monotone missing patterns exist in the data with majority of monotone missing patterns, then the arbitrary missing patterns will be converted to monotone missing patterns under MAR assumption.

##### Step 3. Generation of imputed datasets for AVAL using control-based pattern imputation under MNAR

PROC MI will be used to generate  $m$  complete datasets. The selection of  $m$  depends on the required computing time and will be determined based on the amount of missing information prior to the last patient last visit but has been recommended varying from 5 to 100.

##### Step 4. Convert datasets into long format in which CHG variable represents all change from baseline with different values of avisit.

##### Step 5. Conducting model-based analysis using each imputed dataset

The  $m$  complete datasets are analyzed using MMRM.

Step 6. Pooling the results from the imputed  $m$  datasets for inference

The results from the  $m$  complete datasets are combined to produce inferential results.

### 8.3.3.2.3. Tipping Point Analysis

Another sensitivity analysis – tipping point analysis will be considered to investigate the robustness of the result to departures from the missing at random (MAR) assumption of the MMRM model and to identify the tipping point where the treatment effect in participants with missing data overturns the treatment effect from statistically significant to statistically non-significant.

Hence the tipping point analysis will only be performed if the primary efficacy analysis is statistically significant in treatment effect.

Implementing the tipping point approach includes the following steps ([Yuan 2014, SAS Institute Inc.](#)):

- 1) Under the MNAR assumption, missing SDMT scores up to Day 84 will be imputed using PROC MI under MNAR.
- 2) The imputed values for observations in SAGE-718 treatment group will be adjusted directly using the shift parameter ( $\delta$ ).
- 3) The imputed datasets with the shift parameter applied will be analyzed using PROC MIXED.
- 4) The results will be combined for the inference using PROC MIANALYZE.
- 5) Step 1-4 will be repeated until the result is not statistically significant.
- 6) If needed, step 1-5 will be repeated with more stringent shift parameter applied until the result is not statistically significant.

The shift parameter ( $\delta$ ) value will start from 0 and decrease by 0.2 decrements until non-significant p-value is achieved. One hundred datasets will be generated.

The tipping point summary for each pairwise comparison will include LSmeans difference, the 95% CI, and p-value for each of  $\delta$  value. From  $\delta = (-3, 0)$ , iterations including the tipping point will be summarized.

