## 5.2. Sample Size and Study Power

The study is designed to detect a difference between placebo and the SAGE-718 group in the change from baseline to Day 84 for the primary endpoint, SDMT score. Using a 2-sided test at an alpha level of 0.05, a sample size of approximately 71 evaluable participants per treatment group would provide 90% power to detect a difference of 4 points between SAGE-718 and placebo arms in the change from baseline to Day 84 in SDMT values, assuming that the SD of the change from baseline in SDMT is 7.3 points.

Assuming a 20% dropout and a 1:1 randomization ratio, approximately 178 randomized participants (89 per treatment group) will be required to obtain 71 evaluable participants per treatment group. Evaluable participants are defined as those randomized participants who receive IP and have a valid baseline and at least 1 postbaseline SDMT assessment.

Additional participants may be randomized to ensure a sufficient number of evaluable participants or if the dropout rate is higher than 20%.

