### **Sample SAS Code for Tipping Point Analysis**

```
/*-----*/
```

```
/*--- Generate imputed data set for specified shift parameters ---*/
/*--- data= input data set ---*/
/*--- smin= min shift parameter ---*/
/*--- smax= max shift parameter ---*/
/*--- sinc= increment of the shift parameter ---*/
/*--- out= output imputed data set ---*/
/*-----*/
%macro midata( data=, smin=, smax=, sinc=, out=);
  data &out;
  set _null_;
run;

/*----- # of shift values -----*/
%let ncase= %sysevalf( (&smax-&smin)/&sinc, ceil );
/*----- Imputed data for each shift -----*/
%do jc=0 %to &ncase;
  %let sj= %sysevalf( &smin + &jc * &sinc);
  proc mi data=&data seed=xxx nimpute=m out=outmi;
    class trtp;
    monotone reg(y1 y2 y3);
    mnar adjust( y1 y2 y3 / shift=&sj adjustobs=(trtp='Placebo') ); *active treatment is
    used;
    var trtp y1 y2 y3;
  run;

  data outmi;
    set outmi;
    Shift= &sj;
  run;

  data &out;
    set &out outmi;
  run;
%end;
%mend midata;
```

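### The tipping-point summary range of -3 to 0 conflicts with the open-ended search and, at the design effect, would usually leave the tipping point out of the reported table

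*SAP*

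**What the plan says.** SAP 8.3.3.2.3 plans a tipping-point analysis of SDMT change at Day 84, to be run only if the primary result is significant. Imputed SAGE-718 scores are shifted by delta, and the shifted data sets are analysed and pooled.

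- **Search.** The shift "value will start from 0 and decrease by 0.2 decrements until non-significant p-value is achieved". Step 5 repeats the cycle until the result is no longer significant, and step 6 allows harsher shifts if needed. No lower limit is stated.
- **Summary.** The closing sentence gives the range (-3, 0) and says that "iterations including the tipping point will be summarized".
- **Code.** The sample macro in SAP Appendix B, "macro midata( data=, smin=, smax=, sinc=, out", steps through a fixed grid from `smin` to `smax`. These arguments are left empty, and the macro contains no p-value check and no stopping rule.

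The design figures are in SAP 5.2: "90% power to detect a difference of 4 points between SAGE-718 and placebo arms", "assuming that the SD of the change from baseline in SDMT is 7.3 points", with "a sample size of approximately 71 evaluable participants per treatment group" and 89 per arm randomized to allow for 20% dropout.

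**The concern.** The search rule and the summary rule agree only if the tipping point lies between -3 and 0. A shift applied to a minority of one arm moves the arm mean by only that minority's share of the shift. A shift of -3 is therefore a small perturbation of a trial powered for 4 points.

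Two things are at stake. First, a table confined to (-3, 0) would usually show significant rows only and omit the tipping point. Second, the macro needs `smin` chosen in advance, and -3 is the only lower value the SAP offers. A programmer could run the 16 shifts from 0 to -3 in steps of 0.2 and stop there. At an estimate of 4, SAGE-718 participants imputed under missing at random and then shifted by -3 would still average about 1 point better than placebo, so such a table ends on a mild departure. The analysis runs only after a significant primary result, which is when readers will rely on it.

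**Working it through.** **Inputs.** From SAP 5.2: difference 4, SD 7.3, two-sided alpha 0.05, 71 evaluable and 89 randomized per arm, 20% dropout. From SAP 8.3.3.2.3: the SAGE-718 arm is shifted in steps of 0.2. Assumption: the fraction f of Day 84 scores that is missing equals the 20% dropout rate. The documents give no Day 84 missing rate, and evaluable status needs only one postbaseline SDMT, so a range is shown.

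**The plan's figure.** For difference 4 and SD 7.3, the noncentral t gives power 0.900 at 71 per arm, and 71/0.8 = 88.75, which rounds up to 89. The stated sample size reproduces.

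**Formula.** With n observed per arm, SE = 7.3 × √(2/n) and the critical difference is 1.96 × SE. A shift delta applied to a fraction f of the SAGE-718 arm moves the difference by f × delta. An estimate d therefore tips at delta = -(d - 1.96 × SE)/f.

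**At 20% missing.** n = 89 × 0.8 = 71.2, SE = 1.223, critical difference = 2.40.

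- At delta = -3 the difference is 4 - 0.2 × 3 = 3.40, still well above 2.40.
- The tip at d = 4 is -(4 - 2.40)/0.2 = -8.0.
- Only estimates from 2.40 to 2.40 + 0.60 = 3.00 can tip within the range.
- If the true effect is 4, the chance of significance is 1 - Φ((2.40 - 4)/1.223) = 0.905. The chance of an estimate between 2.40 and 3.00 is 0.111, and 0.111/0.905 is about 12%.
- If the true effect is 3, the same steps give 0.188/0.689, about 27%.

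**Other missing rates** (89 per arm, true effect and estimate 4):

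| Missing at Day 84 | Critical difference | Difference at -3 | Tip | Significant results tipping by -3 |
|---|---|---|---|---|
| 5% | 2.20 | 3.85 | -36.0 | 2% |
| 10% | 2.26 | 3.70 | -17.4 | 4% |
| 20% | 2.40 | 3.40 | -8.0 | 12% |
| 30% | 2.56 | 3.10 | -4.8 | 24% |
| 40% | 2.77 | 2.80 | -3.1 | 37% |

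With 71 per arm as the starting number, the tips at 10%, 20%, 30% and 40% are -14.7, -6.6, -3.8 and -2.2. At an estimate of 4, a tip by -3 needs about 41% missing (89 per arm) or 35% (71 per arm).

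**Check by multiple imputation** (Day 84 values only, Rubin's rules). With 18 of 89 missing per arm and a 4-point difference in the observed data, p at -3 is about 0.006 and the tip is -7.6. With 9 and 27 missing the tips are -14.6 and -5.0. The formula holds the SE fixed, whereas a large shift widens the spread of the completed arm, so the two part most at low missing rates. In 400 simulated trials with a true effect of 4 and 18 missing per arm, 17% of significant results tipped by -3. Formula and simulation together put 83% to 88% outside the range.

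**Carry-forward.** The macro shifts Days 14, 28 and 84, so an earlier shift might feed into Day 84. Assume equal between-visit correlation r of 0.7 to 0.9 and a participant with only Day 14 observed. The Day 28 shift then adds r/(1 + r), or 0.41 to 0.47, of itself at Day 84. A delta of -3 becomes -4.2 to -4.4, still short of -8.

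**The case against.** The strongest reply is that -3 is a display range and not a stopping rule. A reader might infer that the analysis halts at -3 and will usually end with no tipping point found. The documents do not support that. SAP 8.3.3.2.3 states the open-ended search three times, in the decrement rule and in steps 5 and 6, and provides for no such null result. A search run as written would pass -3 and reach the tip. The macro is sample code with empty arguments, so a run cut off at -3 is a risk and not a plan. This part of the reply stands.

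A reader might also infer that robustness to missing-not-at-random dropout would go untested. That is not supported either. SAP 8.3.3.2.2 plans control-based pattern-mixture imputation, which builds the imputation model from placebo participants and so covers the placebo-like dropout case. Its trigger is more than 5% missing in either arm, so it would run at 20%.

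The missing rate is uncertain, and participants who stop treatment are asked to keep attending, so the rate may fall below 20%. That uncertainty does not rescue the range: less missing data moves the tip further from 0, as does any precision gained from baseline adjustment or earlier visits.

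The reply does not dispose of the closing sentence. It says that the summarized iterations include the tipping point and also bounds them at -3. For most significant results at the design effect, both cannot be true.

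**Conclusion.** The point holds as a conflict between the search rule and the summary rule, with a macro that enforces neither. If the true effect is 4 and 20% of Day 84 scores are missing, the tip lies outside (-3, 0) in roughly 83% to 88% of significant results. At an estimate of 4 it is near -8 at 20% missing, about -17 at 10% by formula, about -5 at 30% and about -3 at 40%. The range fits better if the true effect is smaller (about 27% inside at a true effect of 3) or if 35% to 41% or more of the scores are missing.

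The weight is modest. The primary test and the control-based analysis are untouched. What changes is whether the table reports the quantity it was planned to report.

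The macro has a further fault that bears directly on this point. The text shifts SAGE-718, but the code has `adjustobs=(trtp='Placebo')`. Run that way, negative shifts lower placebo and widen the difference: at -3 with 20% missing it becomes 4 + 0.6 = 4.6. No negative delta would then tip the result, however low `smin` is set.

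**What to change.** 1. Replace the closing sentence of SAP 8.3.3.2.3 with: Iterations from delta = 0 through the tipping point will be summarized, with no floor at -3.
2. Set `smin` in the Appendix B macro low enough to reach the tip, or add a p-value stopping rule, so that the code follows the text.
3. Change `adjustobs` to the SAGE-718 arm.
4. Beside the tipping delta, report the implied mean Day 84 change of the imputed SAGE-718 participants and the placebo mean, so that readers can judge plausibility.

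Do not swap one arbitrary floor for another. A bound of -15, for example, would fall short of the formula tip of -17.4 at 10% missing.

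The cost is one SAP sentence, two small code edits and one added table column. Computing is light: reaching -8 in steps of 0.2 takes 8/0.2 + 1 = 41 shifts instead of 16.

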### 8.3.3.3. Supportive Analysis of Primary Endpoint

The primary analysis will be repeated based on the █. No sensitivity analysis will be performed based on the █.

A forest plot of the difference in LS means and 95% CI bar for the changes from baseline to Day 84 on SDMT score using primary analysis, sensitivity analyses (excluding tipping point analysis) and supportive analysis will be provided.

#### 8.3.3.4. Subgroup Analyses of Primary Analysis

Primary endpoint will be analyzed for the following subgroups:

- Age ( $\leq 50, > 50$ )
- Sex (Male, Female, Unknown/Undifferentiated)
- BMI ( $\leq 18.4, 18.5-24.9, 25-29.9, \geq 30 \text{ kg/m}^2$ )
- Country (US, Rest of World)
- Baseline MoCA score ( $< 18, \geq 18$ )
- Baseline UHDRS – Independent scale ( $< 80, \geq 80$ )
- CAP ( $< 100, \geq 100$ )
- [REDACTED]
- [REDACTED]
- [REDACTED]
- Baseline Symbol Digit Modalities Test (SDMT) ( $< M, \geq M$ , where M-Mean value at Baseline in FAS)
- Baseline Trail Making Test B (completed within 240 sec: yes/no)
- Use of ADM (Yes / No)
- Use of Anti-Chorea Medication (Yes / No)
- Use of Anti-Psychotic Medication (Yes / No)

The MMRM analyses will also be provided for change from baseline in primary endpoint within each baseline subgroup level. If any treatment group for any level of subgroup has  $\leq 10$  participants with available CFB at Day 84, the subgroup level will not be used in the analysis.

A forest plot of the difference in LS means and 95% CI bar for the changes from baseline to Day 84 on SDMT score overall and in each subgroup will be provided.

#### 8.3.4. Analysis of Key Secondary Efficacy Variable

The key secondary efficacy endpoints are the change from baseline to Day 84 on 1) UHDRS- Independence Scale; 2) Trail Making B (TMT-B) in a subgroup of participants who were able to complete the test within 240 seconds at Baseline; 3) One Touch Stockings of Cambridge (OTS-MLC) ; 4) Paced Tapping Test (PTAP); 5) Huntington's Disease Everyday Functioning (Hi-DEF) – at home subdomain score; 6) Clinical Global Impression – Severity (CGI-S) – cognitive status subdomain score. These key secondary endpoints will be analyzed similarly to the analysis of primary endpoint.

Plot showing the LS means of key secondary endpoints  $\pm$  SE bar over time within each treatment group will be provided.

### 8.3.5. Multiplicity Adjustment

The statistical comparisons for the primary efficacy endpoint and the key secondary endpoint will be carried out in the fixed-sequence procedure which tests hypotheses in a hierarchical order to control the familywise type I error rate. This means that statistically significant results for the comparison in the higher rank (primary) for no difference between SAGE-718 versus placebo is required to initiate the testing of the next comparison in the lower rank (key secondaries) for no difference between SAGE-718 versus placebo. Since a hierarchical procedure is used, each comparison will be tested at a significance level of 0.05 and an overall alpha level of 0.05 will be preserved. The hierarchical order for the key secondary outcomes is as follows: 1) UHDRS-Independence Scale; 2) Trail Making B (TMT-B) in a subgroup of participants who were able to complete the test within 240 seconds at Baseline; 3) One Touch Stockings of Cambridge (OTS-MLC) ; 4) Paced Tapping Test (PTAP); 5) Huntington's Disease Everyday Functioning (Hi-DEF) – at home subdomain score; 6) Clinical Global Impression – Severity (CGI-S) – cognitive status subdomain score.

### 8.3.6. [REDACTED]

[figure not shown]
[figure not shown]
[figure not shown]

Table 7. [REDACTED]

[figure not shown]
[figure not shown]

Table 8. [REDACTED]

[figure not shown]

[REDACTED]

[REDACTED]  
[REDACTED]

[figure not shown]
[figure not shown]
[figure not shown]
[figure not shown]
[figure not shown]
[figure not shown]
[figure not shown]
[figure not shown]
[figure not shown]
[figure not shown]
[figure not shown]
[figure not shown]
[figure not shown]
[figure not shown]
[figure not shown]
[figure not shown]
[figure not shown]
[figure not shown]
[figure not shown]
[figure not shown]
[figure not shown]
[figure not shown]
[figure not shown]
[figure not shown]
[figure not shown]
[figure not shown]
[figure not shown]
[figure not shown]
[figure not shown]
[figure not shown]
[figure not shown]
[figure not shown]
[figure not shown]
[figure not shown]
[figure not shown]
[figure not shown]
[figure not shown]
[figure not shown]
[figure not shown]
**Table 9:** [REDACTED]

[REDACTED]

For clinician-rated outcomes of symptomatology, analysis will be performed as described in Table 10.

**Table 10. Clinician-Rated Outcomes of Symptomatology**

Assessments	Description	Variable	Analysis
Clinical Global Impression – Severity (CGI-S)	                                                                                                <br		

Generalized estimating equation (GEE) methods will also be used

GEE models will include baseline severity score, treatment, visit, and visit-by-treatment as categorical explanatory variables. An average of CGI-S severity scores [REDACTED] will be considered as a baseline severity score for CGI. The comparison of interest will be the difference between SAGE-718 and matching placebo at the Day 84 time point. Odds ratios and 95% confidence interval will be summarized, and the p-value from the hypothesis test of no difference between the treatment groups will be also presented.

#### 8.4. Safety Analysis

Safety and tolerability of SAGE-718 is a secondary objective of this study. Proportion of participants experienced treatment-emergent adverse events (TEAEs) is one of the secondary endpoints, and change from baseline in vital signs, clinical laboratory analyses, electrocardiograms (ECGs), [REDACTED]

[REDACTED] (Table 11). All safety analysis will be performed on the Safety Set using actual treatment received.

The safety endpoints evaluated at scheduled visits within treatment period are taken as done in nominal visit, without any windowing. If a value is available for a nominal scheduled visit, that value will be used in summary by visit. If scheduled visit value is not available, a value from the specific visit window will be included in summary. For Post-treatment period visits, the choice of the visit will follow the same rule as described in Table 12 and Table 13.

Anytime on treatment, last value on treatment and last value on study will be included in the summaries whenever indicated in the relevant sections below. Anytime on treatment is defined as measurement on or after first dose, on or before the date of last dose. Last value on treatment is defined as the last post-baseline value between first dose of IP (exclusive) and up to the date of last dose of IP (inclusive). Last value on study is defined as the last post-baseline value on or after the first dose of IP and on or before the last date of the study.

No statistical hypothesis testing will be conducted on the safety analyses.

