Abbreviations: AE = adverse event, ASO = anti-sense oligonucleotide; COVID-19 = coronavirus disease 2019; C-SSRS = Columbia–Suicide Severity Rating Scale; ECG = electrocardiogram; ET = early termination; FSH = follicle-stimulating hormone; HD = Huntington’s Disease; Hi-DEF = Huntington’s Disease Everyday Functioning Scale; HIV = human immunodeficiency virus; ICF = informed consent form; IP = investigational product; [REDACTED]; [REDACTED]; [REDACTED]; SAE = serious adverse event; UHDRS = Unified Huntington’s Disease Rating Scale.

Note: If needed, participant-reported outcomes and study partner-reported outcomes can be completed remotely/at home via the web.

- a. Both participants and study partners (if applicable) will be consented during the Screening Period. [REDACTED]
- b. In addition to full medical history, all medications and supplements taken within 8 weeks prior to Screening, all medications used to treat HD (including ASO therapies) regardless of timing, and all nonpharmacological methods (eg, psychosocial, psychotherapeutic) used to treat or prevent neuropsychiatric, functional, and cognitive manifestations of HD are to be recorded. Information regarding diagnosis, isolation, and/or hospitalization due to COVID-19 will be documented as part of medical history, AE collection, and prior/concomitant medication/procedure collection at screening and throughout the study. Confirmed (genetically tested) or suspected family history of HD will be collected.
- c. Participants and study partners (if applicable) will be trained by study staff on the use of software applications and devices necessary for the conduct of the study.
- d. Vital signs to include body temperature, respiratory rate, heart rate, and blood pressure. On dosing days, vital signs will be measured prior to dosing. Blood pressure and heart rate will be measured after the participant has been in the supine position for at least 5 minutes and then repeated approximately 1 and 3 minutes after standing at all scheduled time points. Vital signs can be repeated once per visit if out of range.
- e. A full physical examination is to be conducted during Screening and at Day 112. At other visits, physical examinations will include a brief assessment of general appearance, cardiovascular, respiratory, gastrointestinal, and neurological systems and followed by a targeted physical assessment as needed. A symptom-directed examination may be conducted at any time at the discretion of the investigator.

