- f. Test results of genetically confirmed disease with CAG expansion  $\geq 36$  collected as part of medical history is acceptable in lieu of central laboratory confirmation. For any genetic counseling, the study sites should follow the local practice.

- g. Serum FSH test will be conducted at Screening for the female participants to confirm whether a female participant with  $\geq 12$  months of spontaneous amenorrhea meets the protocol-defined criteria for being postmenopausal.
- h. To include hepatitis B and C screening tests, HIV-1 and -2 antibody.
- i. Single ECG will be measured after the participant has been in the supine position for at least 5 minutes. When ECG measurements coincide with safety assessments, vital signs assessment or blood draws, blood draws should be carried out after ECG and vital signs.
- j. Clinical laboratory assessments will include blood samples for hematology, clinical chemistry, biochemistry, coagulation, serology, genetic testing, and urinalysis. Samples will be collected  $\leq 2$  hours prior to dosing on dosing days. On non-dosing days, collection may occur at any time.
- k. A breath test for alcohol will be performed.
- l. Data on cigarette use will be collected using the question: "How many packs of cigarettes did you smoke over the past 7 days?" at the time points specified.
- m. Serum pregnancy tests will be conducted for all female participants at Screening; urine pregnancy tests will be conducted at other scheduled time points for female participants that are not postmenopausal or permanently sterile.

p. Total Functional Capacity [REDACTED] scores will be collected at Screening, [REDACTED]. Independence Scale will be conducted at [REDACTED] 84 [REDACTED].

r. Cognitive tests at all time points are to be performed at the same time of day ( $\pm 2$  hours) and postdose on dosing days

[figure not shown]
v. On visit Days 1, 14, 28, 56, and 84, participants will self-administer IP in the clinic under the supervision of study staff. All scheduled safety assessments will be conducted prior to dosing and all scheduled cognitive tests will be administered post dosing.

w. Study staff will dispense enough IP for the participant to take daily at home until the next scheduled visit.

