### **8.4.2. Early Termination from the Study**

At the time of study withdrawal/stopping study participation, if possible, an ET visit should be conducted. The participant will be permanently discontinued both from the IP and from the study at that time.

If the participant withdraws consent for disclosure of future information, the sponsor will retain and continue to use any data collected before such a withdrawal of consent.

If a participant withdraws from the study, he/she may request destruction of any samples taken and not tested, and the investigator must document this in the site study records.

Possible reasons for study discontinuation include but are not limited to the following:

- AE
- Pregnancy
- Protocol deviation
- Non-compliance with study drug
- Lost to follow-up
- Withdrawal by subject
- Screen failure
- Study terminated by sponsor
- Physician decision
- Other

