#### 8.4.2. Clinical Laboratory

Clinical laboratory assessments will include blood samples for hematology, clinical chemistry, coagulation, and urinalysis. Samples will be collected  $\leq 2$  hours prior to dosing on dosing days. On non-dosing days, collection may occur at anytime.

Any lab results considered clinically significant by the investigator will be captured as adverse events, hence will show up in AE displays.

All laboratory values will be summarized for the Safety Set using actual treatment received. Results of continuous hematology, clinical chemistry parameters, coagulation, and urinalysis parameters (quantitative) at each scheduled visit and mean changes from baseline will be summarized using standard international (SI) units. In addition, it will also include the summary of last post-baseline values on treatment (on or after first dose, on or before last dose) and on study (on or after first dose, on or before last day of the study).

All laboratory results will be listed in individual participant data listings.

Normal ranges for each parameter will be provided by the laboratory. Shift from baseline to worst post-baseline values in abnormality of results at anytime on treatment, the last value on treatment (on or after first dose, on or before last dose and the last value on study (on or after first dose, on or before last day of the study) in abnormality of results will be summarized. If a participant has both low and high post-baseline records, the participant will be counted twice for each low and high cell.

The number and percentage of participants with potentially clinically significant (PCS) values will be provided in separate displays in hematology, clinical chemistry and liver function tests provided for such occurrence for anytime on treatment, last value on treatment, within 28 Days after the last dose of treatment (follow-up period). PCS values will be identified for specific laboratory parameters as outlined in the table below.

Liver function tests will be monitored closely for PCS values, and will be summarized for occurrence anytime post-baseline for the following parameters for these PCS threshold (for condition involving more than one parameter, the results need to be from the same timepoint):

- Alanine Aminotransferase:  $>3\times\text{ULN}$ ,  $>5\times\text{ULN}$ ,  $>10\times\text{ULN}$
- Aspartate Aminotransferase:  $>3\times\text{ULN}$ ,  $>5\times\text{ULN}$ ,  $>10\times\text{ULN}$

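### SAP 8.4 closes the on-treatment window for laboratory, ECG and vital-sign values on the date of last dose, so dose-withheld and next-day values lose the on-treatment label

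*SAP*

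**What the plan says.** SAP 8.4 (Safety Analysis) states: "Anytime on treatment is defined as measurement on or after first dose, on or before the date of last dose". The last value on treatment ends on the same date. The last value on study runs to the end of the study.

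These windows feed three sections:

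- **SAP 8.4.2 (laboratory).** The shift table covers "Shift from baseline to worst post-baseline values in abnormality of results at anytime on treatment, the last value on treatment" and the last value on study. Potentially clinically significant (PCS) values are shown for any time on treatment, last value on treatment, and within 28 days after last dose.
- **SAP 8.4.3 (QTcF)** and **SAP 8.4.4 (vital signs).** PCS values are shown in the same three rows. SAP Table 11 plans no shift table for ECG or vital signs.

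The timing of the measurements is in the protocol's Table 2 footnotes: "On visit Days 1, 14, 28, 56, and 84, participants will self-administer IP in the clinic under the supervision of study staff", and "All scheduled safety assessments will be conducted prior to dosing and all scheduled cognitive tests will be administered post dosing". For vital signs: "On dosing days, vital signs will be measured prior to dosing". SAP 8.4.2 has laboratory samples taken at most 2 "hours prior to dosing on dosing days". Early termination (ET) is not among the listed supervised-dosing visits.

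For adverse events, SAP 8.4.1 uses a different window: an event is on treatment up to 30 days after the last dose date.

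**The concern.** Dosing is once daily in the morning and safety assessments come first. A scheduled value after Day 1 is therefore read about a day after the previous dose. Under the SAP rule it counts as on treatment only if a dose is taken on that date or later. Two participants with the same exposure and the same time since dose can be classified differently, and the deciding event comes after the measurement and may be caused by it. A vital sign or ECG that leads the investigator to withhold that day's dose, with no later dose, is the clearest case. An ET or unscheduled value obtained the day after the last dose is the other.

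If such values are abnormal more often in one arm, the on-treatment PCS rows understate that arm's rate, and the values sit in a follow-up row beside measurements taken weeks after dosing. At one and the same visit, a symptom would be an on-treatment event while the blood pressure behind it would be a follow-up value.

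**Working it through.** The documents give no figure to reproduce, so the check applies the SAP rules by date. Let *d* be the study day of the measurement and *L* the study day of the last dose.

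- On treatment (SAP 8.4): first dose ≤ *d* ≤ *L*.
- Follow-up PCS row (SAP 8.4.2 to 8.4.4): *L* < *d* ≤ *L* + 28.
- On-treatment adverse event (SAP 8.4.1): *d* ≤ *L* + 30.

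| Case | *d* | *L* | Value | Follow-up PCS row | Adverse event that day |
|---|---|---|---|---|---|
| Day 28 value, dose taken, then stopped | 28 | 28 | on | no | on |
| Day 28 value, result acted on two days later | 28 | 30 | on | no | on |
| Day 28 value, dose withheld, not resumed | 28 | 27 | **off** | yes | on |
| Day 84 completer | 84 | 84 | on | no | on |
| ET on the last-dose date | *L* | *L* | on | no | on |
| ET the next day | *L* + 1 | *L* | **off** | yes | on |
| ET 2 to 28 days after | *L* + 2 to *L* + 28 | *L* | off | yes | on |
| ET 29 or 30 days after | *L* + 29, *L* + 30 | *L* | off | no | on |

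**Time since dose.** Rows 1 and 3 describe the same measurement: Day 28, previous dose on Day 27. Only the later dose differs. A next-day ET value has the same one-day gap. The two bold rows are the misclassified ones. Later ET values are plausibly off treatment.

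**Values available.** At nominal days, laboratory tests and ECGs have two scheduled post-baseline treatment visits, Days 28 and 84. The number counted as on treatment is 0 if *L* < 28, 1 if *L* is 28 to 83, and 2 for completers. Vital signs have Days 14, 28, 56 and 84. With last dose on Day 79 and ET on Day 80, the last scheduled value on treatment goes back to Day 28 for laboratory and ECG, and to Day 56 for vital signs.

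**Shift table.** Take an abnormal laboratory value on Day 28 with *L* = 27, in a participant who stays in the study and is normal on Day 112. Worst on treatment does not include it, since 28 > 27. Nor does last on treatment. Last on study is the normal Day 112 value. The abnormality is in none of the three shift summaries.

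**Follow-up row.** For a completer with *L* = 84, the follow-up visits are 98 − 84 = 14 and 112 − 84 = 28 days after the last dose. A next-day value is pooled with these.

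**Ceiling on the ET route.** The planned dropout gives 178 × 0.20 = 35.6, about 36 participants. Assume that all have an ET visit and that a share *s* take a dose that day; neither is stated. ET assessments outside the window are then 36 × (1 − *s*):

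- *s* = 0: 36
- *s* = 10%: about 32
- *s* = 25%: 27
- *s* = 50%: 18

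Only those seen exactly one day after the last dose are misclassified, and the documents give nothing from which to count them. Dose-withheld values at scheduled visits would be additional and cannot be counted either.

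**The case against.** The other side has a good case, and most of it stands.

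- **Stopping events are captured as adverse events.** Protocol 12.2.1 makes a laboratory, vital-sign or ECG change an adverse event if it results in discontinuation or interruption of treatment. SAP 8.4.1 keeps it on treatment for 30 days and tabulates events leading to IP withdrawal, interruption and dose reduction.
- **The values remain in other tables.** PCS values appear in the 28-day rows. Liver thresholds are counted at any time post-baseline. By-visit summaries use nominal visits or visit windows whatever the dosing status: a Day 80 ET value falls in the Day 84 window for laboratory and ECG (57 to 98) and for vital signs (71 to 91). For someone who leaves at ET, that value is normally the last on study.
- **No half-life is given** from which to justify a particular lag, and the safety analyses involve no hypothesis testing.

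A reader might infer that any abnormal value leading to stopping drops out. The documents do not support that. The bound is an inclusive date, and laboratory samples are drawn shortly before a supervised dose. If the result returns after dosing (turnaround is not stated), the value is dated on or before the last dose and is kept.

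A reader might also infer that nearly every ET value is lost. No interval between last dose and ET is given, and an ET value on a dosing day stays in. Protocol 8.4.2 says of study withdrawal: "The participant will be permanently discontinued both from the IP and from the study at that time". That is compatible with a dose on the ET day.

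Nor can a withheld dose after an abnormal blood pressure or ECG distort a shift table for those measures, because none is planned.

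What the objection does not answer is the classification itself. An adverse-event table does not replace a PCS count, the follow-up row mixes next-day values with later washout values, and the laboratory worst-shift table has no follow-up row.

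**Conclusion.** The point holds in a limited form. The window in SAP 8.4 gives different labels to values at the same time since dose, according to whether a dose follows, and it differs by 30 days from the adverse-event window. The values affected are chiefly vital signs and ECGs acted on at the visit with no later dose, and values from an ET or unscheduled visit the day after the last dose. A laboratory value is affected only if no dose is taken on or after the sampling date; it then enters the shift tables only as the last value on study.

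The size is unknown. The conclusion rests on once-daily morning dosing and pre-dose assessment, both stated in the protocol. It does not rest on any assumed event rate. A reader might infer a particular downward bias in the on-treatment PCS rates, or a distorted ratio between arms. The documents contain no figure for how often abnormal values lead to a withheld dose, so neither can be put as a number. This is a defect in descriptive safety tables and does not touch the primary analysis.

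**What to change.** In SAP 8.4, define both on-treatment windows for laboratory, ECG and vital-sign values as running through the date of last dose + 1 day, which is one dosing interval. Carry this into 8.4.2, 8.4.3 and 8.4.4. In 8.4.2 that includes the shift tables and the places where the window is restated in parentheses. Start the 28-day follow-up rows the day after the new cut-off, at last dose + 2 days, so that no value is counted in both rows.

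This needs no half-life, because it only gives equal labels to values at equal time since dose. It does not align the window with the 30-day adverse-event window, and need not: later ET values stay off treatment.

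The cost is one sentence, the matching edits in 8.4.2 and one programming flag, best made before the first database lock. The downside is that a value taken the day after the last dose counts as on drug, which is the same interval that already applies to the scheduled pre-dose values.
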